1 **A DOUBLE-BLIND, RANDOMIZED STUDY COMPARING STEROID INJECTION AND**
 2 **BIODRESTORE™ FOR PATIENTS WITH KNEE OSTEOARTHRITIS**

3
 4
 5
 6 **Protocol Summary**

Title of Study:	A Double-blind, Randomized Study Comparing Steroid Injection and BioDRestore for Patients with Knee Osteoarthritis
Study Type:	Postmarket Interventional
Primary Investigator:	[name]
Primary Endpoint:	Visual Analog Pain Score (VAS), VR-12, Lysholm, SANE and Knee Injury and Osteoarthritis Outcome Score (KOOS) at the 6-week, 3-month, 6-month, and 12-month post-injection time periods between the two groups.
Secondary Endpoints:	Inflammatory markers at 6 months post-injection.
Design:	Prospective, randomized, two-arm, double-blind study
Length of Study:	12M follow-up
Sample Size:	84 subjects

7
 8
 9 **Schedule of Events**

	BL	TX	6WK	3M	6M	12M
Informed Consent	√	-	-	-	-	-
Inclusion/ Exclusion	√	√	-	-	-	-
Demographics/ Medical History	√	-	-	-	-	-
Randomization	-	√	-	-	-	-
Physical Exam-ROM	√	-	√	√	√	√
Patient Outcomes (VAS, KOOS, Lysholm, SANE, VR-12)	√	-	√	√	√	√
Knee aspiration	-	√	-	-	√	-
X-ray	-	-	-	-	-	√
Adverse Event Assessment	√	√	√	√	√	√

11

12 **1. Background**

13

14 Osteoarthritis (OA), specifically involving the knee, is one of the most common causes of human disease¹
15 and can lead to significant pain and functional decline². A potential element of OA includes degenerative
16 tears of the knee meniscus and/or chondropathy, both of which involve destabilization from mechanical
17 or biological issues³.

18

19 Cortisone injections are commonly used to temporarily relieve inflammation and pain associated with
20 osteoarthritis. The response or effect of the injection can vary, depending on the stage of OA.⁴ Advanced
21 OA where little cartilage remains may not provide enough joint space for the injection to be effective.
22 Cortisone injections can also potentially cause an adverse reaction in certain patient populations,
23 particularly patients with diabetes who may experience a significant increase in blood sugar after a
24 cortisone injection.⁵

25

26 Alternatives to cortisone injections include viscosupplementation, platelet-rich plasma (PRP) injections
27 and stem-cell therapy. One form of therapy that has shown promising results with little reported on in
28 literature is amniotic tissue matrices, to include BioDRestore™ Elemental Tissue Matrix. BioDRestore is
29 a "morselized, flowable tissue allograft derived from amniotic tissues. Amniotic tissues have been shown
30 to support soft tissue repair, reduce inflammation and minimize scar tissue formation".^{6,7}

31

32 This study will compare corticosteroid injection to BioDRestore injection in patients with significant
33 (Kellgren-Lawrence grade 3-4) knee osteoarthritis. Our hypothesis is that BioDRestore will result in
34 better outcomes than corticosteroid when injected intra-articularly in patients with knee OA.

35

36 **2. Study Endpoints**

37

38 Primary Endpoint

- 39 • Visual Analog Score (VAS), VR-12, Lysholm, SANE and Knee Injury and Osteoarthritis
40 Outcome Score (KOOS) at the 6-week, 3-month, 6-month, and 12-month post-injection time
41 periods.

42

43 Secondary Endpoints

- 44 • Inflammatory markers at 6-months post-injection.

45

46 **3. Subject Recruitment and Screening**

47

48 *Screening*

49 Patients who present with osteoarthritis of the knee and are recommended for a knee
50 injection will be screened for inclusion into the study. Following discussion of the
51 study between the patient and the treating physician, the patient will be given the
52 opportunity to move forward with the informed consent process.

53

54 *Enrollment*

55 The subject will be considered enrolled once voluntary informed consent has been
56 given, and the form has been signed and dated by all required parties.

57

58 *Randomization*

59 Subjects will be randomized to a treatment arm (corticosteroid or BioDRestore injection)
60 using a 1:1 ratio. Once study eligibility has been confirmed, the study coordinator or
61 designee will randomize the subject to a treatment arm. The treatment for each subject
62 will be assigned through the study database.

63
64
65
66
67
68
69
70
71
72
73
74
75
76
77
78
79
80
81
82
83
84
85
86
87
88
89
90
91
92
93
94
95
96
97
98
99
100
101
102
103
104
105
106
107
108
109
110
111
112

Blinding

Study subjects and investigators will be blinded to the treatment assignment for the duration of the study to reduce the risk of bias. The research coordinator will provide the randomization to the investigator’s medical assistant (MA) prior to treatment in order for the MA to assist with preparation of the injection.

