3.1. Inclusion Criteria

Subjects must meet all of the following characteristics for inclusion in the study.

- Male or female, aged 18 to 80 years.
- Willing and able to give voluntary informed consent to participate in this investigation.
- Patient presents with knee osteoarthritis and Kellgren Lawrence grade 3-4 (OA diagnosed and confirmed by treating physician using standing x-ray).
- Candidate for intra-articular knee injection.
- BMI < 40

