372 2 groups and five outcome measures, and assuming an effect size of 0.20 (small) based on between group
373 differences we constructed a sample size estimation using a Multivariate Analysis of Variance
374 (MANOVA). Measuring global effects, with an expected 80% power, and a standard error of probability
375 of 0.05, we estimate the need for a minimum sample size of 70 for statistical significance (~35 per group).
376 To account for a 20% drop-out rate, a sample size of 84 subjects will be recruited. We will employ
377 intention to treat and a chains equation, multiple imputation method in which we will assign predictor,
378 structural and impute variables. Further, we will not oversample characteristics within each group for
379 drop-outs.
380
381

382 **11.2 Data Analyses**

383
384 Descriptive statistics will be used to describe both groups at baseline. Appropriate tests of differences will
385 be used to compare baseline differences in descriptive statistics, pain, range of motion, etc., between the
386 two groups (e.g., t-tests and chi-square). Adverse events, including severity of these events will be
387 captured and compared between the two groups. A Multivariate Analysis of Variance (MANOVA) will
388 be used to measure differences between the targeted outcome measure at each of the given timepoints
389 (baseline, 6-week, 3-month, 6-month, and 12-months post-injection time periods). A MANOVA
390 investigates the effects of a categorical predictive variable (groups) on 2 or more continuous outcomes,
391 which are correlated and represented by a vector of dependent variables. For all analyses, a p value of
392 <0.05 will be considered statistically significant.
393
394
395
396
397

398 **12. Bibliography**

- 399 1. Divine J, Zazulak B, Hewett TE. Viscosupplementation for knee osteoarthritis. Clin Orthop Rel
400 Res. 2006; 455:113-122.
- 401 2. Dawson J, Linsell L, Zondervan K, et al. Epidemiology of hop and knee pain and its impact on
402 overall health status in older adults. Rheumatology. 2004; 43:497-504.
403

404 3. Laupattarakasem W, Laopaiboon M, Laupattarakasem P, Sumananont C. Arthroscopic
405 debridement for knee osteoarthritis (Review). Cochrane Collaboration. Issue 4, 2009.
406 4. Younes M, et al. Systemic effects of epidural and intra-articular glucocorticoid injections in
407 diabetic and non-diabetic patients. *Joint Bone Spine*. 2007, 74(5): 472-6.

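### Osteoarthritis grade (Kellgren-Lawrence 3 or 4) appears neither as a covariate in the MANOVA nor as a named randomization factor, although the background says response to cortisone can vary with stage

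*Combined protocol and SAP*

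**What the plan says.** - **Section 1 (Background).** In its paragraph on cortisone, the protocol states: "osteoarthritis. The response or effect of the injection can vary, depending on the stage of OA". It then gives a possible mechanism for advanced disease: "OA where little cartilage remains may not provide enough joint space for the injection to be effective".
- **Section 3.1 (Inclusion Criteria).** Both grades are eligible: "Patient presents with knee osteoarthritis and Kellgren Lawrence grade 3-4". The treating physician confirms this on a standing x-ray.
- **Section 3 (Randomization).** Subjects are allocated "using a 1:1 ratio" after eligibility is confirmed, and the treatment "will be assigned through the study database". No stratification factor, block scheme or minimization is named.
- **Section 11.2 (Data Analyses).** The MANOVA "investigates the effects of a categorical predictive variable (groups) on 2 or more continuous outcomes". Group is the only predictor and no covariate is listed. Simple tests will "be used to compare baseline differences in descriptive statistics, pain, range of motion, etc., between the" two arms, but no adjustment follows from them. No analysis by grade is planned.

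**The concern.** The protocol's rationale singles out disease stage as something that may alter the response to one of the two treatments. Its eligibility rule then admits two stages, and neither the allocation nor the model takes account of which one a subject has.

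If grade also predicts the outcome scores, two things follow in a trial of 84 subjects. The arms may differ by chance in their share of grade 4, which makes a single result harder to interpret. The spread between grades also stays in the error term, which costs some power. If the planned baseline tests then showed a grade difference, any adjustment would be post hoc and open to dispute.

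**Working it through.** **Inputs from Section 11.1.** Effect size 0.20, two groups, five outcome measures, 80% power, alpha 0.05, minimum N = 70 (about 35 per group), 84 recruited (42 per arm at 1:1).

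**Inputs not in the documents, so assumed.**
- q, the share of subjects with grade 4: 0.3 to 0.5.
- d, the difference in outcome between grades 3 and 4 in within-grade SDs: 0.2, 0.5 or 0.8.

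**Step 1: reproduce the plan's figure.** Section 11.1 does not name the effect-size metric. Read it as f² = 0.20 in a MANOVA global-effects test with five responses and two groups. Then df1 = 5, df2 = N − 6 and noncentrality = N × f². At N = 70, df2 = 64 and the noncentrality is 70 × 0.20 = 14. Power is 80.1%, and 70 is the smallest N that reaches 80%. The stated figure is reproduced. It neither uses nor depends on grade, so this point disputes no number in the plan.

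**Step 2: chance imbalance without stratification.** Treat the grade 4 counts in the two arms as independent binomials with 42 subjects each, and sum the exact joint probabilities. A gap of at least 10 points means a difference of at least 5 subjects (5/42 = 11.9%). A gap of at least 15 points means at least 7 subjects (7/42 = 16.7%).

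| Share with grade 4 | Gap of 10 points or more | Gap of 15 points or more |
|---|---|---|
| 0.3 | 28% | 12% |
| 0.4 | 32% | 15% |
| 0.5 | 33% | 16% |

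An even mix is the worst case; at q = 0.8 the figures fall to 22% and 7.5%. A normal approximation without continuity correction gives 36% and 17% at q = 0.5, which is too high.

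**Step 3: what an imbalance does to one score.** The shift in the unadjusted arm difference is imbalance × d. For 15 points this is 0.15 × 0.2 = 0.03 SD, 0.15 × 0.5 = 0.075 SD, or 0.15 × 0.8 = 0.12 SD. The standard error of the arm difference at 42 per arm is √(2/42) = 0.218 SD, so the middle value is 0.075/0.218 = 0.34 of a standard error.

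**Step 4: what adjustment gains.** The variance explained by grade is R² = q(1−q)d² / [1 + q(1−q)d²]. Adjustment raises f² to at most 0.20/(1−R²) and uses one error degree of freedom (df2 = 63 at N = 70). For q = 0.5 and d = 0.5, R² = 0.0625/1.0625 = 0.059, f² = 0.2125, noncentrality = 70 × 0.2125 = 14.875, and power is 82.7%.

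| d | R² (q = 0.3 to 0.5) | Power at N = 70, adjusted | N for 80% power |
|---|---|---|---|
| 0 | 0 | 80.0% | – |
| 0.2 | 0.008–0.010 | 80.4–80.5% | 70 |
| 0.5 | 0.050–0.059 | 82.3–82.7% | 67 |
| 0.8 | 0.118–0.138 | 85.5–86.3% | 62–63 |

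The unadjusted comparator is 80.1%. The row d = 0 shows the price if grade has no effect.

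**The case against.** **The background sentence is about cortisone.** A reader might infer that the protocol calls grade a known prognostic factor. It does not. It makes a hedged statement about response to one of the two treatments, which suggests possible effect modification. Nothing says that grade predicts VAS, KOOS, Lysholm, SANE or VR-12 whatever the treatment. This stands, and it limits the remedy: a main-effect covariate does not address effect modification.

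**Randomization already protects validity.** A reader might take chance imbalance for bias. It is not: under randomization it is already reflected in the standard error, and type I error is not inflated. This stands. What remains is precision, and confidence in one small trial.

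**Grade may not be on file, and adjustment is not free.** A reader might assume that the exact grade is already collected. Section 3.1 requires only confirmation of the band 3-4, and the Schedule of Events lists an x-ray only at 12 months. The fix therefore needs one added data item and one error degree of freedom. Both are small.

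**Baseline scores may do most of the work.** All five outcomes are measured before injection, and baseline is one of the MANOVA time points. If the comparison is of change, a constant difference between grades largely cancels and the gain in Step 4 shrinks. Section 11.2 does not settle this.

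**Silence is not exclusion.** Section 3 does not rule out stratification in the study database. That is correct, but if the database does stratify, the protocol should say so and the model should reflect it.

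**Conclusion.** The point holds as a modest improvement. The protocol gives a reason to attend to disease stage, enrols two stages, and uses stage neither in the stated model nor in the stated allocation. No figure in the plan is wrong and no passages contradict each other.

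The gain in power runs from about 0.3 to 6 percentage points over assumed grade differences of 0.2 to 0.8 SD. It is large only at the top of that range, and those figures are upper values because they take no account of baseline scores. The imbalance probabilities rest on an assumed grade mix. The documents do not support a claim that the planned comparison is invalid or biased, or that grade is an established predictor of these outcomes. Severity: nice to have.

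**What to change.** 1. State that the exact grade (3 or 4) is read from the eligibility x-ray and entered in the study database before randomization. Cost: one data item.
2. Pre-specify grade as a covariate in the Section 11.2 model. Cost: one error degree of freedom, which takes power from 80.1% to 80.0% if grade has no effect. This remains worthwhile if recruitment has begun, provided that the exact grade can be taken from the eligibility film.
3. Optional, if recruitment allows: randomize 1:1 in permuted blocks of concealed size within each grade. Two strata are manageable with 84 subjects. Cost: two lists instead of one.
4. Optional: report a treatment-by-grade estimate with its confidence interval, labelled exploratory and low-powered. This is the only item here that addresses whether the treatment contrast differs by stage.

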3.1. Inclusion Criteria

Subjects must meet all of the following characteristics for inclusion in the study.

- Male or female, aged 18 to 80 years.
- Willing and able to give voluntary informed consent to participate in this investigation.
- Patient presents with knee osteoarthritis and Kellgren Lawrence grade 3-4 (OA diagnosed and confirmed by treating physician using standing x-ray).
- Candidate for intra-articular knee injection.
- BMI < 40

3.2. Exclusion Criteria

Subjects with any of the following characteristics must be excluded from participation in the study:

- Patients who have received intra-articular injection(s) in the last 3 months.
- Patients who have undergone arthroscopic surgery on the study knee in the past year.
- Patients who have undergone arthroplasty on the study knee.
- Ligament instability
- Diabetes (Type 1 or II)
- Inflammatory arthropathies.
- Fibromyalgia or chronic fatigue syndrome.
- Female patient who is pregnant or nursing.
- Chronic use of narcotics.
- Any other reason (in the judgment of the investigator).

3.3. Withdrawal of Subjects from Study

Voluntary Withdrawal by Subject

Study participation is voluntary and subjects may withdraw at any point during the study. If a subject withdraws from the study, the investigator will make all reasonable efforts to determine the reason for the subject’s withdrawal and will document the reason on the applicable form and in the patient’s medical record. After a subject withdraws from the study, no effort will be made to replace or follow the subject. However, the subject will still be offered clinical management of their knee condition.

Withdrawal by Investigator

The investigator may withdraw subjects from the study for many reasons, including but not limited to the following:

- Occurrence of a serious adverse event
- Investigator’s discretion to withdraw subject for safety reasons
- Subject noncompliance with visits and/or assessments
- Subject is lost to follow-up (as defined below)

113
114
115
116
117
118
119
120
121
122
123
124
125
126
127
128
129
130
131
132
133
134
135
136
137
138
139
140
141
142
143
144
145
146
147
148
149
150
151
152
153
154
155
156
157
158
159
160
161

Lost to Follow-Up

Subjects will be defined as lost to follow-up when the following procedures have been documented in the subject's source documentation:

- At least 2 phone calls made on separate dates to the subject are not returned
- A letter is sent to the subject's last known address and the subject does not reply after 30 days.

4. Informed Consent

Investigators are responsible for obtaining and documenting the voluntary informed consent of the study subjects prior to conducting any study-related assessments per 21 CFR Part 50. Prior to beginning the trial the investigator must obtain written and dated approval of the informed consent form. Subjects will receive a copy of the initial signed and dated informed consent form prior to the subjects' participation in the trial and any revised informed consent forms during the duration of the trial.

The subject must sign and date the consent form in the presence of the investigator, who must sign and date the consent form in the presence of the subject. The communications with the subject regarding informed consent process (initial and subsequent) should be documented in the medical record.

5. Study Procedures

Study Assessments

Visit 1- Baseline Assessment

The following information will be collected at the time of enrollment:

- Informed Consent
- Medical History & Demographics
- Patient Outcomes: Subject to complete VAS, VR-12, KOOS, Lysholm and SANE prior to injection.
- Range of Motion Assessment: Measurement taken using goniometer.

Visit 2- Randomization & Procedure

- **Inclusion/Exclusion review**
- **Randomization**
- Procedure: For patients with current knee effusion, the investigator will drain the effusion prior to the injection. For subjects that do not exhibit any signs of knee effusion, the investigator will proceed with the injection. Study subjects will be randomized to receive a cortisone or BioDRestore injection. Subjects will be blinded to the assignment. Prior to the injection, the area will be prepared with sterile solution and numbing agent. Next, an injection of one of the following treatments, dependent on randomization, will be injected into the articular space of the knee:

_2 cc of 40 mg/ml Kenalog with 3 cc of saline

_2 cc BioDRestore with 3 cc of saline

Knee arthrocentesis (for procedure, see below under "Follow-up Visits"): The study doctor will attempt to perform a knee aspiration to provide a delta value for the assay.

Follow-Up Visits (6WK, 3M, 6M, 12M)

The following information will be collected at each follow-up visit:

- 162 • Patient Outcomes: Subject to complete VAS, VR-12, KOOS, Lysholm, and SANE scales
163 • **6-month only, subject will return to the clinic for the following:**
164 ▪ Range of motion assessment
165 ▪ Knee arthrocentesis (aspiration): The area will first be prepared with sterile
166 solution and numbing agent. Using a 10-mL syringe, obtain at least
167 0.25mL of synovial fluid via a parapatellar approach. A knee aspiration
168 attempt will be made on all subjects that produced an adequate sample at
169 baseline prior to the injection. Upon completion, the syringe will be
170 labeled and transported to the Clemson Bioengineering Laboratory of
171 Orthopaedic Tissue Regeneration & Orthobiologics lab for analysis.
172 ▪ Aspirate analysis: Enzyme linked immunosorbent assay (ELISA) will be
173 performed on synovial fluid aspirated from the knees of study patients at 6
174 months post-injection to determine if there are quantitative differences in
175 soluble mediators and products of osteoarthritis. Briefly, synovial fluid
176 samples will be evaluated in duplicate for inflammatory (interleukin-1 beta;
177 IL-1 β and tumor necrosis factor-alpha; TNF- α), anti-inflammatory
178 (interleukin-1 receptor agonist; IL-1RA and interleukin-10; IL-10), pain
179 (prostaglandin-E₂; PGE₂) and soluble signals which indicate cartilage
180 damage (S100A8 and S100A9 proteins, respectively).
181
182 Briefly, frozen (-80°C) samples will be thawed and analyzed using a
183 bicinchoninic acid assay (BCA) to normalize for total protein content.
184 Samples will be diluted accordingly using calibrator diluent supplied with
185 ELISA kits. ELISA will be performed according to manufacturer's protocols
186 and well plates will be analyzed optically on a μ -Quant microplate reader.
187 Concentrations will be determined using a standard curve developed from
188 known concentrations of supplied analyte. Experimental sample analyte
189 concentrations (ng/ml) will be plotted on histograms and group mean
190 concentrations \pm standard deviation will be calculated for each experimental
191 group.
192 • **12-month only, subject will return to the clinic for the following:**
193 ○ Range of motion assessment
194 ○ Radiographs of affected knee
195 • **Allowed Concomitant Medications and Prohibited Treatments**
196 ○ Concomitant Medications: Patients are allowed acetaminophen and/or ibuprofen
197 for the first 6 months following treatment.
198 ○ Prohibited Treatments: Oral steroids, steroid injections and Viscosupplementation
199 are not permitted for the first 6 months of the study in the treated knee.
200

201 6. Risk Analysis

202 *Potential Risks*

203 Mild pain and discomfort at the injection site are normal and expected reactions. While
204 rare, complications may occur due to either the cortisone injection or study injection.

205 These include the following:

- 206 • Infection
- 207 • Post-injection flare
- 208 • Localized subcutaneous or cutaneous atrophy
- 209 • Skin discoloration
- 210 • Stiffness

211
212
213
214
215
216
217
218
219
220
221
222
223
224
225
226
227
228
229
230
231
232
233
234
235
236
237
238
239
240
241
242
243
244
245
246
247
248
249
250
251
252
253
254
255
256
257
258

Potential Benefits

Participation in this study may offer no benefit to subjects. However, it is possible that the use of BioDRestore will result in better outcomes than corticosteroid when injected intra-articularly in patients with knee OA.

Study subjects will receive a \$50 stipend for each study visit for a total of \$300 if all visits are completed.

7. Adverse Events

Definitions

An adverse event is defined as any untoward medical occurrence in a clinical investigation in which a subject is administered a study device and which does not necessarily have a causal relationship with the device. An adverse event can therefore be any unfavorable and unintended sign (including an abnormal laboratory finding or an abnormal radiographic finding), symptom, or disease temporally associated with the use of study device, whether or not related to the study device. The following are specific definitions of adverse events:

Adverse Event (AE) — any untoward medical occurrence in a subject, regardless if there is a relationship between the AE and the device.

Adverse Reaction (AR)- The FDA requires, per 21CFR 1271.350(a), the reporting of certain adverse reactions related to implantation, transplantation, infusion or transfer of an HCT/P. For tissue products, an Adverse Reaction is any unintended response, including a communicable disease, in the recipient of a human tissue or cell product implantation or transplantation. An Adverse Reaction is considered serious (SAR) if it meets the criteria of a Serious Adverse Event (see below).

Serious Adverse Event (SAE) — an adverse event that:

- leads to a death
- leads to a serious deterioration in the health of a subject that results in a life-threatening illness or injury
- results in a permanent impairment of a body structure or a body function
- requires in-subject hospitalization or prolongation of existing hospitalization
- results in medical or surgical intervention to prevent permanent impairment to body structure or a body function
- results in congenital anomaly/birth defect

Treatment for Adverse Events

In the event of an adverse event, the investigator and/or other professional personnel in attendance will provide whatever appropriate medical treatment is indicated for the problem.

Documentation of Adverse Events

All adverse events will be documented in the source documentation. Beginning after the study procedure has taken place, all AE's, including those measured, observed or volunteered, will be recorded on the applicable case report form. The investigator will review all documentation (e.g., hospital progress notes, laboratory, or diagnostic reports)

259 relative to the event being reported. The investigator will then record all relevant
260 information regarding an AE onto the study CRF.

261
262 The investigator will attempt to establish a diagnosis of the event based on signs,
263 symptoms, and/or other clinical information. In such cases, the diagnosis should be
264 documented as the AE and not the individual signs and symptoms.

265 When reporting an AE, the investigator will evaluate the event for duration, intensity,
266 relationship and outcome.

267
268 Examples of an AE:

- 269 ▪ Exacerbation of a chronic or intermittent pre-existing condition including either
270 an increase in frequency or intensity of the condition.
- 271 ▪ Significant or unexpected worsening or exacerbation of the condition/indication
272 under study.
- 273 ▪ A new condition detected or diagnosed after study device administration even
274 though it may have been present prior to the start of the study.
- 275 ▪ Pre- or post-procedure events that occur as a result of protocol-mandated
276 procedures (e.g., invasive protocol-defined procedures, modification of a
277 subject's previous treatment regimen).

278
279 An AE Does NOT Include:

- 280 ▪ Medical or surgical procedures. The medical condition that leads to the
281 procedure is the AE.
- 282 ▪ Hospital admissions where an untoward medical occurrence did not occur.
- 283 ▪ Day to day fluctuations of pre-existing disease or conditions present or detected
284 at the start of the study that do not worsen.
- 285 ▪ The condition/indication being studied or expected progression, signs, or
286 symptoms of the condition/indication being studied unless more severe than
287 expected for the subject's condition.
- 288 ▪ Post-operative findings of swelling or pain within two (2) weeks of the initial
289 procedure, unless deemed by the physician as of greater severity than expected.

290
291 *Follow-Up of Adverse Events*

292 After the initial AE report, the investigator is required to proactively follow each subject
293 until the event resolves. All AEs documented at a previous visit that are designated as
294 ongoing will be reviewed at subsequent visits/contacts.

295
296 Adverse events will be followed until resolution, until no further changes in the event are
297 expected (i.e. the point at which a subject experiencing a critical adverse event is treated
298 successfully and stabilized even though he/she may continue to experience lingering
299 sequelae that may never resolve), until the subject is lost to follow-up, or until it is agreed
300 that further follow-up of the event is not warranted (e.g. non-serious, study therapy
301 unrelated, mild or moderate adverse events ongoing at the subject's final study visit).

302
303 **8. Reporting of Adverse Events**

304 *Investigator Adverse Event Reports*
305

306 Investigators are responsible for reviewing all SAEs and determining the relationship to
307 the treatment and documenting on the appropriate CRF. All SAEs must be reported by
308 the investigator to the IRB as soon as possible, but no later than ten (10) working days
309 after learning of the event. The investigator must submit a detailed report that will
310 identify the description of symptoms, classification of the event, date of onset, severity,
311 treatment, and outcome. Supporting medical records may be obtained as an adjunct to an
312 adverse event report and placed in the subject's study file.

313 All AEs will be categorized as mild, moderate or severe based on the following
314 definitions:

315 Mild: The subject is aware of the sign or symptom, but finds it easily tolerated. The
316 event is of little concern to the subject and/or little clinical significance. The event is not
317 expected to have any effect on the subject's overall health or wellbeing.

318 Moderate: The subject has discomfort enough to cause interference with or change in
319 usual activities. The event is of some concern to the subject's health or wellbeing and
320 may require medical intervention and/or close follow-up.

321 Severe: The adverse event interferes considerably with the subject's usual activities. The
322 event is of definite concern to the subject and/or poses substantial risk to the subject's
323 health or wellbeing. The event is likely to require medical intervention and/or close
324 follow-up and may be incapacitating or life threatening. Hospitalization and treatment
325 may be required.
326

327
328 Should an AR or SAE occur, an investigator must submit to DermaSciences and to the reviewing IRB a
329 report of the event as soon as possible, but in no event later than 48 hours after the investigator first learns
330 of the AR or SAE.

331
332 Reported ARs and Serious Adverse Events will be reviewed and investigated per Standard Operating
333 Procedures. Upon a receipt and evaluation of an AR or SAE, Derma Sciences will report the results of
334 such evaluation to FDA and to all reviewing IRBs and participating investigators within 10 working days
335 after receipt of first notice of the AR or SAE. Thereafter, the Sponsor will submit such additional reports
336 concerning the effect per FDA and/or IRB requests.
337

338 339 **9. Source Documentation**

340 Investigators are responsible for obtaining and maintaining complete subject health information in the
341 medical record for each subject and each assessment in the protocol (source documents). Source
342 documents include all information in original records and certified copies of original records of clinic
343 findings, observations or other activities in the study necessary for the reconstruction and evaluation
344 of the trial. Source data are contained in source documents (e.g., hospital records, clinic and office
345 charts, memoranda, dispensing records, subject questionnaires, clinic evaluation transcriptions,
346 operative notes, x-rays, radiology reports, blood collection and shipment records, research subject
347 files, etc.)
348

349 **10. Disclosure of Data and Data Security**

350 351 *Data Security and Confidentiality*

352 The clinical data obtained in this study will be kept private. In any sort of published
353 report, there will be no identifying information. Records for this study may be reviewed

354 by the IRB and/or other government agencies may inspect and photocopy all medical
355 records applicable to involvement in this study.
356

357 Participating subjects will be asked to sign a consent form that includes an authorization
358 to use and/or disclose personal health information. Subjects are free to refuse
359 authorization to transfer personal information. If the subject chooses not to agree to this
360 authorization, the subject is not eligible to participate in the study. Personal information
361 (including sensitive personal health information, such as medical history) if relevant to
362 the study will be reviewed, collected in a computer database, stored in electronic or
363 manual files, audited, and / or otherwise processed by the investigator, regulatory
364 agencies, and other persons and/or agencies as required by law or allowed by applicable
365 regulations.

366 **11. Statistical Procedures**

367 **11.1 Sample Size Estimate**

368
369 To determine sample size, we powered the study (a-priori) for the primary outcome measures of VAS,
370 VR-12, KOOS, Lysholm, and SANE scales at baseline, 6-week, 3-month, 6-month, and 12-month post-
371 injection time periods. Assuming normal distributions among the 2 independent groups' 5 time-points for
372 2 groups and five outcome measures, and assuming an effect size of 0.20 (small) based on between group
373 differences we constructed a sample size estimation using a Multivariate Analysis of Variance
374 (MANOVA). Measuring global effects, with an expected 80% power, and a standard error of probability
375 of 0.05, we estimate the need for a minimum sample size of 70 for statistical significance (~35 per group).
376 To account for a 20% drop-out rate, a sample size of 84 subjects will be recruited. We will employ
377 intention to treat and a chains equation, multiple imputation method in which we will assign predictor,
378 structural and impute variables. Further, we will not oversample characteristics within each group for
379 drop-outs.
380
381

382 **11.2 Data Analyses**

383
384 Descriptive statistics will be used to describe both groups at baseline. Appropriate tests of differences will
385 be used to compare baseline differences in descriptive statistics, pain, range of motion, etc., between the
386 two groups (e.g., t-tests and chi-square). Adverse events, including severity of these events will be
387 captured and compared between the two groups. A Multivariate Analysis of Variance (MANOVA) will
388 be used to measure differences between the targeted outcome measure at each of the given timepoints
389 (baseline, 6-week, 3-month, 6-month, and 12-months post-injection time periods). A MANOVA
390 investigates the effects of a categorical predictive variable (groups) on 2 or more continuous outcomes,
391 which are correlated and represented by a vector of dependent variables. For all analyses, a p value of
392 <0.05 will be considered statistically significant.
393
394
395
396
397

398 **12. Bibliography**

- 399 1. Divine J, Zazulak B, Hewett TE. Viscosupplementation for knee osteoarthritis. Clin Orthop Rel
400 Res. 2006; 455:113-122.
- 401 2. Dawson J, Linsell L, Zondervan K, et al. Epidemiology of hop and knee pain and its impact on
402 overall health status in older adults. Rheumatology. 2004; 43:497-504.
403

404 3. Laupattarakasem W, Laopaiboon M, Laupattarakasem P, Sumananont C. Arthroscopic
405 debridement for knee osteoarthritis (Review). Cochrane Collaboration. Issue 4, 2009.
406 4. Younes M, et al. Systemic effects of epidural and intra-articular glucocorticoid injections in
407 diabetic and non-diabetic patients. *Joint Bone Spine*. 2007, 74(5): 472-6.
